#### 10.4.1.4. Exploratory Efficacy Endpoints

The exploratory efficacy endpoints are defined in [Section 3.4](#). The change in total sBA from Week 3 (primary endpoint) to delivery will be considered, and the difference between treatment groups will be tested using a randomization-based version of rank analysis of covariance (ANCOVA; [Stokes et al. 2012](#)). In a similar manner, the change from baseline in total sBA concentration to the time of delivery will also be explored. An additional analysis will be performed that examines the change from baseline to delivery but that averages across the last 2 time points on or prior to delivery. Similar analyses will be performed for Adult ItchRO. Associations between the changes from baseline to Week 3 in total sBA and Adult ItchRO will be assessed using either Pearson’s or Spearman’s correlation coefficient. “Responder” analyses for composite perinatal outcomes will be performed using baseline sBA and ItchRO and the change at Week 3 values in sBA and ItchRO as covariates and, separately, using the Week 3 values themselves (instead of the change at Week 3).

Change in biomarkers of bile acid synthesis, inflammation, and pruritogens as well as the proportion of participants with sBA <40 µmol/L at the end of the treatment period will also be explored. The change in biomarkers will follow the same approach as other exploratory efficacy endpoints described above. The proportion of participants with sBA <40 µmol/L at the end of the treatment period will be analyzed in the same manner as the secondary efficacy endpoint for composite perinatal outcomes.

Further exploratory efficacy endpoints include continuous and binary endpoints on additional perinatal outcomes. The analysis of continuous endpoints will follow the same approach as other exploratory efficacy endpoints described above. Binary outcomes will be analyzed in the same manner as the secondary efficacy endpoint for composite perinatal outcomes. Additional details will be included within the SAP.

The secondary endpoint of composite perinatal outcomes will also be explored using an ordinal scale, with ranks assigned according to the severity of the outcomes specified within [Section 3.2](#).

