## 1. PROTOCOL SUMMARY

### 1.1. Synopsis

Name of Sponsor/Company: Mirum Pharmaceuticals, Inc.	
Name of Investigational Product: Volixibat	
Name of Active Ingredient: Volixibat potassium (formerly SHP626 and LUM002)	
Protocol Number: VLX-401	
Title of Study: A Phase 2a/2b Randomized Double-Blind Placebo-Controlled Study to Evaluate the Efficacy and Safety of Volixibat in Adult Women with Intrahepatic Cholestasis of Pregnancy and Elevated Serum Bile Acid Concentrations (OHANA)	
Study Centers: This study will be conducted at multiple sites across Australia, New Zealand, North America, and the United Kingdom. Other regions may be added.	
Participants: Up to 280 participants will be enrolled in this study. 

Part 1 (open label): Up to 80 participants with serum bile acid (sBA) <math>\geq 10</math> <math>\mu\text{mol/L}</math> during the screening period or at any time during the current pregnancy will be enrolled.

Part 2 (double blind): Approximately 200 participants with a screening sBA level <math>\geq 20</math> <math>\mu\text{mol/L}</math> will be enrolled (100 per arm).

	
Randomization: Part 1 (open label): 

1:1 (volixibat 20 mg twice daily [BID]/volixibat 80 mg BID)

 Part 2 (double blind): 

1:1 (selected volixibat dose BID/placebo BID)

 Randomization will be stratified according to background use of ursodeoxycholic acid (UDCA) or not (in Part 1), gestational age at randomization, presence/absence of gestational diabetes, and highest sBA levels before randomization (in Part 2).	
Study Period: 2020 to 2024	Study Phase: 2a/2b

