## 5.6. Replacement Strategy

A participant who discontinues from study drug or withdraws from the study will not be replaced.

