## 10.1. Sample Size Determination

Part 1 of the study is designed for estimation without formal statistical testing; hence, there are no formal power considerations. For example, with 20 participants per group and assuming a standard deviation of 25 for each group, a 95% CI for the mean for each volixibat arm would have a half width of 11.

For the power calculations for Part 2, it is assumed that only a single dose will be selected at the end of Part 1, and a 2-sided alpha 0.05 will be used to test whether there is a difference between the 2 groups. Thus, for Part 2, a sample size of 100 participants per arm has 80% power to detect mean difference of 10 with standard deviation of 25. Power was calculated using SAS, version 9.4.

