##### **10.4.2.1. Adverse Events**

In general, TEAEs are defined as AEs that start or deteriorate on or after the first dose of study medication and no later than 7 days following the last dose of study medication. For any participants (i.e., expectant mothers) who die during the study and the date of death is between the date of the first dose of study medication and the date of study discontinuation (as entered by the site), inclusive, all AEs (including those resulting in death) that occur during the study will be considered as TEAEs irrespective of the last dose and will be included in the TEAE summaries. All summaries of AEs will be based on TEAEs unless specified otherwise.

The complete list of Preferred Terms for AESIs and ECIs (as described in [Sections 9.2.6](#) and [9.2.7](#)) will be outlined in the SAP and summarized.

AEs will be coded using MedDRA. The number and proportion of participants who experience the event according to MedDRA System Organ Class (SOC) and Preferred Term will be presented by treatment group.

The incidence of all AEs and treatment-related AEs will be tabulated by treatment received. These AEs will be classified by SOC and Preferred Term using MedDRA. AEs will be graded using the CTCAE, Version 5.0, grading scale. For incidence reporting, if a participant reported >1 AE that was coded to the same SOC or Preferred Term, the participant will be counted only once for that specific SOC or Preferred Term. An overview of AEs and TEAEs, both of which include participant incidence of AEs, treatment-related AEs, AEs by severity, AESIs, ECIs, SAEs, deaths, and AEs that lead to discontinuation, will be presented.

Furthermore, exposure-adjusted incidence rates (EAIR) will be provided for each AE reported. For EAIR analyses, the following convention will be used to calculate the denominator (i.e., population-level time at-risk) for these analyses. The population-level time at-risk includes only the time each participant is at risk. The start date of at-risk time is the date of first dose of study drug, and the last date of at-risk time is the start date of the occurrence of the AE or is censored at completion/early termination, whichever is earlier.

While no formal hypothesis testing or margin selection is planned, the risk difference and corresponding exact 95% CI (using the method of Chan and Zhang [1999]) will be presented to compare treatment groups with regards to AESIs and ECIs.

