- $SE(P_1 - P_2) = \sqrt{\frac{\sum w_h^2 \left[ \frac{p_{1h}^*(1-p_{1h}^*)}{n_{1h}-1} + \frac{p_{2h}^*(1-p_{2h}^*)}{n_{2h}-1} \right]}{(\sum w_h)^2}}$ , where  $p_{1h}^* = \frac{m_{1h}+0.5}{n_{1h}+1}$  and  $p_{2h}^* = \frac{m_{2h}+0.5}{n_{2h}+1}$ .  $m_{1h}$  and  $m_{2h}$  are the number of participants who are “responders” in treatment groups 1 and 2 in stratum  $h$ .
- $\alpha = 0.05$
- $Z_{(1-\alpha/2)} = Z_{0.975} = 1.95996$  is the 97.5th percentile of the normal distribution

Note that if the computed lower confidence bound is less than -1, the lower bound is defined as -1. Similarly, if the computed upper confidence bound is greater than 1, the upper bound is defined as 1. Furthermore, as supportive analyses, a Logistic Regression (LR) estimator approach (Ge et al. 2011), as well as a logistic regression model with baseline sBA, gestational age, and presence/absence of gestational diabetes as covariates will be run. The model assumptions of the logistic regression model are not considered a concern because a randomized study has comparable distributions of the treatment groups for covariates and factors for stratification, although they may impact the interpretation of estimated parameters for the covariates. Most importantly, a logistic regression model addresses estimands that are conditional on the covariates in the model, with these estimands sometimes being called participant-specific, and express the extent of efficacy of a treatment that a participant might expect on the basis of her covariates, although they tend to be further from the null for an effective treatment than population average estimand. A randomization-based version of logistic regression will also be considered. It is robust to model assumptions and it has a population average estimand that is the same as the unadjusted odds ratio for comparing two treatments (Zink and Koch 2012).

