### 6.3. Exploratory Efficacy Endpoints

The exploratory efficacy endpoints are defined in [Section 1.1.3](#).

Continuous endpoints will be summarized using descriptive statistics. A p-value will be computed for between treatment comparisons using a van Elteren (vE) test (van Elteren 1960). The Wilcoxon–Mann–Whitney (WMW) test (Mann and Whitney 1947; Wilcoxon 1945) is widely used nonparametric approach to compare two treatments. In the

presence of stratum factors such as gestational age or ItchRO(Obs) Score, the van Elteren test, a stratified WMW test, can be used to adjust for the stratification factors. It was shown by Qu et al. (2008) that vE test preserves the type I error rate regardless of the existence of the stratum effects, and is better than the WMW test when the stratum effects are large.

A non-strata adjusted 95% CI for the difference in means between treatment groups will also be presented. A test of equality of variances will be performed. If the null hypothesis that the variances are equal is rejected, then the 95% CI will be constructed using a Satterthwaite approximation. Otherwise, the variances will be pooled.

For categorical endpoints, the number and percent for each category will be displayed. For responder-type analyses, within a treatment group, an approximate 95% CI will be presented using a stratified Wilson confidence interval (Yan and Su 2010). A 95% CI comparing two treatment groups based on stratum-adjusted MH proportions as described in Section 6.2 will also be generated. A stratified CMH test will be used to calculate the p-value for the difference between treatment groups. The method is applicable to the following endpoints:

- Proportion of participants with an early term delivery (37–38 weeks 6 days, inclusive)
- Proportion of participants with a full-term delivery ( $\geq 39$  weeks)
- Proportion of participants experiencing a perinatal death
- Proportion of participants with a spontaneous preterm delivery
- Proportion of participants with an iatrogenic preterm delivery attributable to ICP
- Proportion of neonates requiring neonatal intensive care unit (NICU) admission for  $\geq 12$  hours between birth and hospital discharge
- Proportion of neonates with meconium-stained amniotic fluid at delivery
- Proportion of participants requiring rescue medication for ICP
- Proportion of neonates with Apgar score  $< 7$  at 5 minutes of life
- Proportion of neonates with umbilical cord pH  $< 7.0$  at birth

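### SAP 6.3 gives perinatal death, Apgar <7 and cord pH <7.0 an interval whose per-stratum +0.5 terms make it too wide when events are rare, so that it can contradict the CMH p-value beside it

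*Protocol*

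**What the plan says.** Protocol 10.4.1.4 covers the additional perinatal outcomes in one sentence: "Binary outcomes will be analyzed in the same manner as the secondary efficacy endpoint for composite perinatal outcomes". It leaves details to the SAP. The Protocol's own method for the composite (10.4.1.3) is a stratified CMH test with supportive logistic models, and no interval formula is given there.

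The interval comes from the SAP. SAP 6.3 lists perinatal death, Apgar <7 at 5 minutes and umbilical cord pH <7.0 among the outcomes concerned, gives them a stratified CMH p-value, and adds: "A 95% CI comparing two treatment groups based on stratum-adjusted MH proportions as described in Section 6.2 will also be generated". SAP 6.2 defines that interval as the Mantel-Haenszel weighted risk difference plus or minus 1.96 standard errors. The difference uses the raw proportions. The standard error replaces each stratum proportion by `p* = (m + 0.5)/(n + 1)`, in both arms, with strata numbered 1 to 12.

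No sparse-data rule is given for these outcomes. For AESIs and ECIs, by contrast, Protocol 10.4.2.1 and SAP 7.1.7 state that "the risk difference and corresponding exact 95% CI (using the method of Chan and Zhang [1999]) will be presented to compare treatment groups".

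**The concern.** A term of +0.5 per stratum does little harm when each stratum holds several events. When most strata hold none, it dominates the variance: an empty cell with 8 participants is treated as a rate of 0.5/9 = 5.6%, and this is repeated in every stratum of each arm. The point estimate does not receive the same adjustment, so the interval is centred on the raw difference with error bars that belong to a much more frequent event.

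The three outcomes are likely to be sparse. Protocol 4.3.2.1 justifies the composite by saying that each single event category is too infrequent to power the study. Protocol 10.4.1.1 expects few or no perinatal deaths before Week 3. Perinatal death also belongs to the composite, and Protocol 8.3.1 and 9.1.1 keep composite events out of AE and SAE reporting. The comparison in SAP 6.3 therefore carries much of the arm-level information on the gravest fetal outcome. A reader would see a small p-value next to an interval that includes zero, with nothing in the plan to say which to believe.

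**Working it through.** **Inputs.** Protocol 10.1: "a sample size of 100 participants per arm has 80% power to detect mean difference of 10 with standard deviation of 25", two-sided alpha 0.05. SAP 6.2: weights, standard error and 12 strata. Assumed because the documents do not give them: single-outcome rates of 0.5% to 2%, and equal strata.

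**The plan's own figure.** 10/(25 x sqrt(2/100)) = 2.83, and subtracting 1.96 leaves 0.87, so power is 0.807, or 0.804 by noncentral t. The stated 80% reproduces. The documents state no width for the binary interval.

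**Formula.** With H equal strata of n per arm the weights cancel and

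`SE = (1/H) x sqrt( sum of p*(1 - p*)/(n - 1) over all 2H cells )`.

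Take 12 strata of 8 per arm (96 per arm):

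- empty cell: (0.5/9) x (8.5/9) / 7 = 0.00750
- cell with one event: (1.5/9) x (7.5/9) / 7 = 0.01984

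With k events in one arm, in k different strata, and none in the other:

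`SE = (1/12) x sqrt( k x 0.01984 + (24 - k) x 0.00750 )`.

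**No events in either arm.** SE = sqrt(0.180)/12 = 0.0353, half-width 6.9 points. The Miettinen-Nurminen score interval is about +/-3.9, a ratio of 1.8.

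**Against the true sampling SD**, `sqrt(2p(1 - p)/100)`, with 12 equal strata and 100 per arm:

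| Rate | SAP half-width (points) | 1.96 x true SD | Ratio |
|---|---|---|---|
| 0.5% | 6.88 | 1.96 | 3.5 |
| 1% | 7.09 | 2.76 | 2.6 |
| 2% | 7.50 | 3.88 | 1.9, or 2.0 with 12 strata of 8 |
| 5% | | | 1.4 |
| 30% | | | 1.04 |

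Simulated coverage at 0.5% to 2% is 100%. Against the score interval, the ratio of mean half-widths is 1.7, 1.6 and 1.5 at 0.5%, 1% and 2%.

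**Number of strata.** With no events and 100 per arm, the SAP half-width is 6.65 points with 12 strata, 5.46 with 8, 3.89 with 4, 2.76 with 2 and 1.96 with 1, against 3.7 for the score interval. With 8 strata the ratio to the true SD is 2.9, 2.2 and 1.7 at 0.5%, 1% and 2%.

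**Agreement with CMH.** With one event in each of k strata, all in one arm, CMH has observed minus expected k/2 and variance k/4, so chi-square = (k/2)^2/(k/4) = k. For 12 strata of 8:

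| Events | CMH p | Fisher p | Difference (points) | SAP 95% CI |
|---|---|---|---|---|
| 6 v 0 | 0.014 | 0.029 | 6.25 | -2.0 to +14.5 |
| 8 v 0 | 0.005 | 0.007 | 8.33 | -0.3 to +17.0 |
| 9 v 0 | 0.003 | | 9.38 | +0.6 to +18.2 |

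At 6 v 0 the score interval is +2.3 to +13.0 and Chan-Zhang is about +1.8 to +13.0. CMH, Fisher, score and exact methods agree, and only the SAP interval differs. It first excludes zero at 9 v 0. With 8 strata of 12 it still includes zero at 7 v 0, where CMH p = 0.008.

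In simulation with true rates of 0% and 5%, about 90% of CMH-significant trials had an SAP interval that included zero. With 30% and 45% it was about 2%.

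**The case against.** The strongest reply is that the size of the effect depends on the strata, and the strata are not settled. SAP 6.2 counts 12, but the factors it names (gestational age, baseline ItchRO, gestational diabetes) give 2 x 2 x 2 = 8 with the two ItchRO bands of SAP 3.4. Twelve matches the 2 x 2 x 3 allocation factors of Protocol 6.3.1. The divisor n - 1 also leaves the standard error undefined when a stratum has one participant in an arm. Under an assumed uneven split this occurred in about 76% of simulated trials with 12 strata and 29% with 8. Strata might therefore be collapsed, and with 4 the interval is close to the score interval at 0 v 0 and just excludes zero at 6 v 0. This stands. The fault is not independent of the choice of strata, although it does occur with every stratum well filled at 8 or 12.

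A second reply is that little depends on this interval. The outcomes are exploratory and outside the testing hierarchy. Counts, within-arm Wilson intervals and the CMH p-value are shown with it, perinatal death has the top score in the ordinal analysis, and the IDMC sees unblinded fetal safety data. An over-wide interval cannot falsely rule out harm. This limits the consequence but does not make the interval right.

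A reader might infer that any clear excess of perinatal death would be reported with an interval including zero. The figures do not support that. The conflict needs roughly 4 to 8 events against 0, and at 9 v 0 the SAP interval excludes zero. At 4 v 0 and 5 v 0 Fisher is not significant either (0.12 and 0.059), so 6 to 8 v 0 is the firm case. If both arms share a rate of 0.5% to 2%, CMH is significant in only about 0.2% to 3% of trials.

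**Conclusion.** The concern holds in a limited form. Applied as written, SAP 6.3 gives wrong error bars for perinatal death, Apgar <7 and cord pH <7.0. With 12 strata, about 100 per arm and assumed rates of 0.5% to 2%, the standard error is about 2.0 to 3.5 times the true SD (1.7 to 2.9 times with 8 strata). Against a score interval, which an analyst could actually report, the excess width is about 1.5 to 1.8 times. It is small with 4 strata or fewer.

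Two wider readings are not supported. The multiplier is not a general property of the interval: it falls to 1.4 at a 5% rate and to about 1.04 at an assumed 30%, so the composite is barely affected, and its hypothesis test is CMH in any case. Nor does the Protocol prescribe the faulty interval: 10.4.1.4 points to the composite's method, and the +0.5 formula is in the SAP alone. The Protocol's remark on few perinatal deaths concerns the period before Week 3 and gives no rate for any of the three outcomes.

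**What to change.** Change SAP 6.3. Protocol 10.4.1.4 need only refer to it.

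- Name perinatal death, Apgar <7 and cord pH <7.0 in advance as low-count outcomes. Add any other binary perinatal outcome whose total over both arms is below a number fixed in the SAP before unblinding, for example 10. A pooled total does not use the difference between arms.
- For these outcomes report counts with the exact Chan-Zhang risk-difference interval already specified for AESIs and ECIs.
- Take the p-value from the same exact unconditional test, as twice the smaller one-sided value. Pairing the interval with Fisher would bring a disagreement back: at 4 v 0 and 5 v 0 the exact unconditional one-sided p is 0.023 and 0.013 (doubled, 0.046 and 0.026), so the interval excludes zero, while Fisher gives 0.12 and 0.059.
- Keep the stratified CMH test and interval for the common outcomes.

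The cost is a paragraph of SAP text and reuse of a procedure the SAP already needs. No extra data are required. The small downside is that the rare-outcome comparison is no longer stratified.

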**Table 4 Perinatal Outcome Severity Scoring**

Perinatal Outcome	Score
Perinatal death	4
Spontaneous preterm delivery	3
Iatrogenic preterm delivery attribute to ICP or ICP-related complications	2
Neonatal unit admission for ≥12 hours from birth until hospital discharge for any of the reasons listed in Section 3.2	1
No perinatal outcome	0

ICP=intrahepatic cholestasis of pregnancy.

The score is assigned according to the most severe outcome following the order shown above. If a participant experiences perinatal death, spontaneous preterm delivery, or iatrogenic preterm delivery attributed to ICP or ICP-related complications AND neonatal unit admission for  $\geq 12$  hours from birth until hospital discharge for any of the reasons listed in [Section 3.2](#), the score will be adjusted by 0.5. For example, if a participant has spontaneous preterm delivery followed by a neonatal unit admission, the score would be  $3+0.5=3.5$ , where the 3 comes from the spontaneous preterm delivery and the 0.5 comes from the fact that neonatal unit admission occurred. This will be analyzed using a stratified log rank test that provides more weight to the more severe outcomes and will employ a randomization-based covariance adjustment ([Zinc and Koch 2012](#)).

Additional, nonefficacy exploratory endpoints are described within [Section 10.4.3](#).

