### 3.2. Secondary Objectives and Endpoints

The following secondary objectives and endpoints are applicable in Part 1 and Part 2.

- To assess the efficacy of volixibat on pruritus due to ICP on the basis of the following endpoint:
  - Mean change from baseline to Week 3 of the treatment period in the weekly average worst daily itch score as measured by the Adult Itch Reported Outcome (ItchRO)
- To assess the impact of volixibat on a composite perinatal outcome in participants with ICP on the basis of the following endpoints:
  - Proportion of participants experiencing one or more of the following:
    - Perinatal death, defined as in utero fetal death after randomization or known neonatal death up to 28 days after birth
    - Spontaneous preterm delivery, defined as delivery at <37 weeks' gestational age following spontaneous onset of preterm labor or preterm premature rupture of the membranes (PPROM)
    - Iatrogenic preterm delivery attributable to ICP or ICP-related complications, defined as delivery at <37 weeks' gestational age resulting from medical intervention (i.e., augmentation/induction of labor or cesarean delivery without prior spontaneous onset of preterm labor or PPROM with one or more of the following as the indication for delivery):
      - Diagnosis of ICP with or without suspected fetal compromise
      - Persistently elevated/increasing sBA
      - Worsening hepatic function
      - Intolerable maternal ICP symptoms
    - Neonatal unit admission for  $\geq 12$  hours from birth until hospital discharge for one or more of the following indications:
      - Respiratory insufficiency/failure with requirement for oxygen supplementation
      - Noninvasive or invasive respiratory support
      - Hemodynamic instability or shock requiring clinical intervention
      - Metabolic acidosis or signs of asphyxia

- Proven infection
- Hypoglycemia or feeding problems requiring intravenous (IV) fluids or tube feeding
- Meconium-stained amniotic fluid and/or its sequelae (e.g., meconium aspiration, etc.)

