**Table 6 Perinatal Outcome Severity Scoring**

Perinatal Outcome	Score
Perinatal death	4
Spontaneous preterm delivery	3
Iatrogenic preterm delivery attribute to ICP or ICP-related complications	2
Neonatal unit admission for $\geq 12$ hours from birth until hospital discharge for any of the reasons listed in Section 1.1.3	1
No perinatal outcome	0

The score is assigned according to the most severe outcome following the order shown above. If a participant experiences perinatal death, spontaneous preterm delivery, or iatrogenic preterm delivery attributed to ICP or ICP-related complications AND neonatal unit admission for  $\geq 12$  hours from birth until hospital discharge for any of the reasons listed in [Section 3.2](#), the score will be adjusted by 0.5. For example, if a participant has spontaneous preterm delivery followed by a neonatal unit admission, the score would be  $3+0.5=3.5$ , where the 3 comes from the spontaneous preterm delivery and the 0.5 comes from the fact that neonatal unit admission occurred. This will be analyzed using a stratified log rank test that provides more weight to the more severe outcomes and will employ a randomization-based covariance adjustment ([Zink and Koch 2012](#)).

Change in biomarkers of bile acid synthesis, inflammation, and pruritogens as well as the proportion of participants with sBA  $<40$   $\mu\text{mol/L}$  at the end of the treatment period will also be explored. The change in biomarkers will follow the same approach as other exploratory efficacy endpoints described above. The proportion of participants with sBA  $<40$   $\mu\text{mol/L}$  at the end of the treatment period will be analyzed in the same manner as the secondary efficacy endpoint for composite perinatal outcomes.

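### In the exploratory perinatal severity score, the extra 0.5 for neonatal unit admission also applies to deaths, so in a singleton pregnancy a stillbirth (4.0) ranks as milder than a neonatal death after a qualifying admission (4.5)

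*Protocol*

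**What the plan says.** The ordinal score is an exploratory re-analysis of the composite perinatal outcome, "with ranks assigned according to the severity of the outcomes" (protocol 10.4.1.4). Table 4 gives perinatal death 4, spontaneous preterm delivery 3, iatrogenic preterm delivery related to ICP 2, a qualifying neonatal unit admission alone 1, and no outcome 0. The base rule is "The score is assigned according to the most severe outcome following the order shown above".

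An adjustment follows: "If a participant experiences perinatal death, spontaneous preterm delivery, or iatrogenic preterm delivery attributed to ICP or ICP-related complications AND neonatal unit admission" for at least 12 hours and a listed reason, then "the score will be adjusted by 0.5". The rule gives no sign, but its worked example adds: "the 0.5 comes from the fact that neonatal unit admission occurred". SAP 6.3 (Table 6) carries the same rule. Neither document caps the score at 4 or exempts deaths.

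Two definitions in protocol 3.2 matter here. The death component is a single category: "Perinatal death, defined as in utero fetal death after randomization or known neonatal death up to 28 days after birth". The admission component requires at least 12 "hours from birth until hospital discharge for one or more of the following indications".

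On the analysis, the SAP says: "This will be analyzed using a stratified log rank test that provides more weight to the more severe outcomes".

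**The concern.** For preterm delivery the extra 0.5 orders outcomes sensibly, because a preterm infant who also needs the neonatal unit has done worse than one who does not. For death it works differently. The 0.5 is open only to an infant who is born alive and survives long enough to complete a qualifying admission. Among singleton deaths it therefore separates those who could be admitted from those who could not, and puts the earliest deaths lower on the scale.

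If treatment turned a stillbirth into a live birth with a qualifying admission and then a death, the participant's score would rise from 4.0 to 4.5 and count as a worse result. If one arm had a stillbirth and the other a neonatal death after admission, this test would favour the arm with the stillbirth. Neither document gives a reason for that order.

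**Working it through.** **1. Reproduce the plan's own figure.** Score = highest base score, plus 0.5 if a death or a preterm delivery occurs together with a qualifying admission. Spontaneous preterm delivery followed by admission: 3 + 0.5 = 3.5, as both documents state.

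**2. Apply the same rule to deaths (singleton pregnancy).**

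| Outcome | Qualifying admission possible? | Score |
|---|---|---|
| Stillbirth, with or without preterm delivery | No | 4.0 |
| Newborn death before 12 hours | No | 4.0 |
| Later neonatal death, no qualifying admission | Possible, did not occur | 4.0 |
| Neonatal death after a qualifying admission | Yes, occurred | 4 + 0.5 = 4.5 |

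The remaining scores (3.5, 3, 2.5, 2, 1, 0) are in a sensible order.

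**3. Score gap in the test.** The documents do not define the log-rank scores or the handling of ties. I assume the usual form for N = 200 (100 per arm): the i-th lowest outcome gets a(i) = Σ 1/(N − j + 1) over j = 1 to i, minus 1, averaged over ties.

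- One death of each kind: the top score is 5.878 − 1 = 4.878 and the second is 4.878 − 1 = 3.878. The gap is 1.0. If the two were tied, both would score 4.378.
- Two deaths of each kind: the 4.5 group averages (4.878 + 3.878)/2 = 4.378. The next two scores are 3.878 − 1/2 = 3.378 and 3.378 − 1/3 = 3.045, which average 3.211. The gap is 1.167. If all four were tied they would share (4.378 + 3.211)/2 = 3.795.

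These gaps depend only on N and the number of deaths.

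**4. Size relative to the test's standard error.** With 100 per arm, the difference between the arms' score sums has SE = √[Σa² × N/(N − 1)]. The documents give no expected outcome rates, so the distributions below are assumptions. The calculation ignores stratification and covariate adjustment.

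- Central case: 140 at 0, 15 at 1, 12 at 2, 8 at 2.5, 8 at 3, 13 at 3.5, 2 at 4 and 2 at 4.5. Σa² ≈ 175.4 (SD of scores √(175.4/200) = 0.94), so SE = √(175.4 × 200/199) = 13.3. A discordant pair (one death of each kind, in opposite arms) shifts the statistic by 1.167/13.3 = 0.09 SE. With one death of each kind and 142 at 0, SE = 13.2 and the shift is 1.0/13.2 = 0.08 SE.
- One participant in ten with any outcome (180, 6, 4, 2, 2, 4, 1, 1 in the same order): SE = 11.5, shift 1.0/11.5 = 0.09 SE. With two deaths of each kind (180, 5, 3, 2, 2, 4, 2, 2) the shift is 1.167/11.5 = 0.10 SE.
- Half with any outcome (100, 30, 24, 14, 14, 16, 1, 1): SE = 13.6, shift 1.0/13.6 = 0.07 SE.

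The range is about 0.07 to 0.10 SE per discordant pair.

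**The case against.** The best defence is that the 0.5 records a second component of the composite on top of the worst one. On that reading 4.5 means death plus admission, just as 3.5 means preterm delivery plus admission. Perinatal death comes first in the list, so the drafting may be deliberate, and how to rank deaths is partly a value judgement. It is fair to say that this is not a contradiction between passages. But the scale is described as a severity ranking, stillbirth and neonatal death are defined as one category, and the second component is unavailable to a singleton that dies before it can be admitted. Counting it does not measure severity among deaths.

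The second defence is that little depends on it. That stands. Every death counts once in the binary composite (protocol 10.4.1.3), perinatal death is also analysed as its own proportion (protocol 3.4, SAP 6.3), and the ordinal score is outside the hierarchy in protocol 10.4.1.2.

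A reader might also infer more than the text supports:

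- That every later neonatal death scores 4.5. It does so only after a qualifying admission.
- That a stillbirth can never receive the 0.5. The score is per participant and Part 1 admits twins, so a stillbirth with an admitted co-twin would literally score 4.5. The statement holds for singletons.
- That the protocol regards stillbirth as worse than neonatal death. It stresses stillbirth risk in its rationale but does not rank the two.

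**Conclusion.** The point holds as a minor defect in a stated scoring rule. Read literally, both documents place a singleton stillbirth, or a death before 12 hours, half a point below a neonatal death after a qualifying admission, and neither gives a reason. The ordering follows from the text alone.

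The size does rest on assumptions: a conventional form of log-rank scores, 100 participants per arm, and illustrative outcome rates. Under these, one discordant pair moves the test by roughly a tenth of a standard error or less. Deaths should be few, so the result of this analysis would rarely change. No confirmatory conclusion is affected, and stillbirths are not hidden, since other planned analyses count all perinatal deaths alike. The case for acting is that the ordering is hard to defend and very cheap to correct before unblinding.

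**What to change.** In protocol 10.4.1.4 (below Table 4) and SAP 6.3 (below Table 6), delete perinatal death from the sentence on the 0.5, so that the adjustment applies only to spontaneous or iatrogenic preterm delivery. Add a short clause that any perinatal death scores 4 whatever else occurred. Without it, a neonatal death after preterm delivery and admission could still be read as 4.5 through the preterm delivery. All other scores stay as they are.

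The cost is a few words in each document. The one loss is that the score no longer separates death alone from death after admission. If the sponsor wants that distinction, it should say so and give the severity rationale.

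While editing the SAP text, correct its cross-references: it points to SAP 1.1.3 and 3.2 for the admission reasons, which are listed in SAP 1.1.2.
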